6.6.4 Subgroup Analyses

The results of selected efficacy variables will be summarized within subgroups using descriptive statistics. The following variables will be used to define subgroups:

- Sex (male vs. female)
- Age at baseline (< 45 vs. \geq 45 years)
- CAG repeat length (< 43 vs. \geq 43)
- Stage at baseline (I, II, III)
 - Stage III will be considered only if there are enough patients.

Additional exploratory analyses of efficacy results may be performed using an ANCOVA model, similar to the primary analysis, based on change from baseline for the variable of interest, with baseline score (not for analysis by baseline stage), CAP score, CAG repeat length (not for analysis by CAG repeat length), treatment, subgroup, and treatment-by-subgroup interaction as covariates.

6.6.5 Exploratory Efficacy Analysis

The exploratory efficacy endpoints are identified in Section [2.1.3](#).

The exploratory endpoints will be summarized using tables, listings, and graphs, as appropriate. Additional statistical modeling may be considered (e.g., ANCOVA, logistic regression).

6.6.6 Historical Controls

Should the treatment discontinuation rate in the placebo arm be significantly higher than expected, the Sponsor may consider the use of historical controls for efficacy analysis. In this scenario, the use of historical controls will be deemed supportive analyses.

Prior to database lock, the Sponsor may select historical controls from ENROLL-HD. These historical controls may be selected to match patients with regard to important baseline characteristics (e.g., gender, CAG, age, IS, International Standard Classification of Education). The objective for use and exact algorithm for selecting historical controls will be specified in the SAP. If implemented, the actual selection will be made before database lock and *unblinding of treatment allocation and will be documented and stored in the Sponsor's database.*

Whether the Sponsor will decide to use those the historical controls, the exact algorithm for borrowing and for deriving an overall treatment effect will be described in the SAP before unblinding.

Additionally, given that some of the patients who will be enrolled in this study may have been part of ENROLL-HD, the Sponsor may explore a within-patient comparison for the

rate of decline in cUHDRS or TFC score, before treatment with RO7234292 (prior to randomization, using ENROLL-HD registry data) and after treatment with RO7234292 (after randomization, using study data), for patients who were randomized to the active arm and had follow-up in ENROLL-HD of at least 1 year's duration prior to randomization into this study.

6.7 SAFETY ANALYSES

The *safety* population (see Section 6.1) will be the primary population for all analyses of safety data. Incorrect treatment assignments (patients who received a treatment different than their planned randomized treatment) will be summarized and the impact on the safety assessment will be discussed.

For all safety analyses, patients enrolled prior to implementation of the Version 4 of the protocol will be summarized separately.

All verbatim adverse event terms will be mapped to MedDRA thesaurus terms. The adverse event severity grading scale indicated in [Table 4](#) will be used for assessing adverse event severity. Laboratory values determined as an adverse event should be graded as per [Appendix 5](#), which is based on the NCI CTCAE (v5.0).

All safety data, including adverse events, laboratory tests, CSSR-S, MoCA, ECG, and vital signs will be reported in individual listings and summarized by treatment for each assessment time using descriptive statistics. For continuous variables, both the original value as well as the change from baseline will be reported.

The incidence of adverse events will be summarized on the basis of body systems and dictionary preferred terms. The incidence of adverse events by severity and relationship to study drug or study procedure and incidence of marked abnormal laboratory test results will be provided.

The iDMC will review safety data throughout the study. Analyses required for the iDMC data review will be performed as described in the iDMC Charter.

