5.1.1.1 Post-Lumbar Puncture Syndrome

RO7234292 will be delivered directly to the CNS by IT lumbar puncture injection. Post-lumbar puncture syndrome (e.g., headaches, nausea, vomiting, infection, hemorrhage, nerve irritation pain) can occur with IT administration. Experience to date with post-lumbar puncture syndrome, as reported in the *completed* Phase I/Ia study, includes headache, which occurred after 10% of procedures and was transient and mild in the vast majority of patients. *In the ongoing Phase II OLE Study BN40967 (9-month*

RO7234292—F. Hoffmann-La Roche Ltd

75/Protocol BN40423, Version 4

data), 4 events of post lumbar puncture syndrome were reported in the Q4W cohort (17.4%) and 3 in the Q8W cohort (13.0%). All these events were rated as mild and resolved without treatment with the exception of 1 event in the Q4W cohort that required treatment (mild and resolved).

Patients should walk post-lumbar procedure, to assist drug distribution (see Section 4.3.2.1); however, if a patient develops a headache after the lumbar puncture with characteristic features, which makes walking intolerable, the patient should be encouraged to first sit down and if the headache persists then lie in a comfortable position, which is most likely in the supine position owing to the postural nature of the symptoms. Supportive treatment may include rehydration, consumption of caffeinated drinks, simple analgesics, opioids, and antiemetics. If these conservative measures fail, more specific measures may be indicated.

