5.3.4 Assessment of Causality of Adverse Events

Investigators should use their knowledge of the patient, the circumstances surrounding the event, and an evaluation of any potential alternative causes to determine whether an adverse event is considered to be related to the study drug, indicating "yes" or "no" accordingly. The following guidance should be taken into consideration (see also [Table 5](#)):

- Temporal relationship of event onset to the initiation of study drug
- Course of the event, with special consideration of the effects of dose reduction, discontinuation of study drug, or reintroduction of study drug (as applicable)
- Known association of the event with the study drug or with similar treatments
- Known association of the event with the disease under study
- Presence of risk factors in the patient or use of concomitant medications known to increase the occurrence of the event
- Presence of non-treatment-related factors that are known to be associated with the occurrence of the event

Table 5 Causal Attribution Guidance

Is the adverse event suspected to be caused by the study drug on the basis of facts, evidence, science-based rationales, and clinical judgment?	
YES	There is a plausible temporal relationship between the onset of the adverse event and administration of the study drug, and the adverse event cannot be readily explained by the patient's clinical state, intercurrent illness, or concomitant therapies; and/or the adverse event follows a known pattern of response to the study drug; and/or the adverse event abates or resolves upon discontinuation of the study drug or dose reduction and, if applicable, reappears upon re-challenge.
NO	An adverse event will be considered related, unless it fulfills the criteria specified below. Evidence exists that the adverse event has an etiology other than the study drug (e.g., preexisting medical condition, underlying disease, intercurrent illness, or concomitant medication); and/or the adverse event has no plausible temporal relationship to administration of the study drug (e.g., cancer diagnosed 2 days after first dose of study drug).

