6.6.1 Estimands

Following the very recent estimand framework outlined in the ICH-E9 draft addendum (FDA 2017), the attributes of the estimand for the primary endpoint are defined as follows:

- Population: ITT population (see Section 6.1)
- Variable: Change from baseline in cUHDRS score at Week 101
 - Note: cUHDRS scale will be replaced by TFC scale for the FDA.
- Intercurrent events (ICEs):
 - Treatment discontinued for study drug-related reasons (e.g., treatment-related adverse event or lack of efficacy):

After treatment discontinuation, the actual off-treatment values will be used in the analysis.

- Treatment discontinued for NSDR reasons (e.g., lost to follow-up):

After treatment discontinuation, imputed hypothetical values as if patients had continued receiving study drug will be used in the analysis. In this instance, any data collected after treatment discontinuation will not be included in the analysis.
- Population level summary: Difference in mean change from baseline at Week 101 between each active arm and the placebo arm

The primary estimand is a combination of a treatment-policy strategy and a hypothetical strategy (FDA 2017) to account for the different assumptions for each type of ICE.

The Sponsor will emphasize to investigators the importance of collecting data for the primary endpoint through Week 101, even if patients discontinue study drug but do not withdraw study consent, as well as the importance of providing detailed reasons for treatment discontinuation. The primary estimator, described by the statistical model in Section 6.6.2, will be applied on the dataset produced after multiple imputation of *any missing value*. *In principle*,

- *missing data as well as off-treatment data from patients who discontinued treatment for NSDR reasons will be imputed from patients with available data from the same treatment arm collected while on treatment*
- *missing data from patients who discontinued treatment for SDR reasons will be imputed from:*
 - *patients with available data from the placebo arm collected either while on treatment or off treatment and*
 - *patients with available data from the same treatment arm collected while off treatment*

Multiple imputation of missing data values will be performed as follows:

1. **Imputation step:** *Missing data values will be imputed "m" times leading to "m" complete datasets.*

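### Section 6.7 promises adverse event incidence by relation to the study procedure, but the protocol defines a causality judgment for the study drug only

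*Protocol*

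**What the plan says.** Section 6.7 of the protocol plans to report "The incidence of adverse events by severity and relationship to study drug or study procedure", alongside summaries by body system, preferred term and treatment arm.

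Section 5.3 requires three assessments for each recorded event: seriousness, severity and causality. Causality is to follow Section 5.3.4, where the investigator must "determine whether an adverse event is considered to be related to the study drug", yes or no. Table 5 puts the same single question: "Is the adverse event suspected to be caused by the study drug on the basis of facts, evidence, science-based rationales, and clinical judgment". Under Table 5 an event counts as related unless it meets stated exceptions. One exception reads "Evidence exists that the adverse event has an etiology other than the study drug", and its examples are "preexisting medical condition, underlying disease, intercurrent illness, or concomitant medication". The lumbar puncture and the intrathecal injection are not among them.

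Other sections assume that a judgment about the procedure exists. Section 5.5.1 asks for follow-up to a final outcome of serious events considered related to the drug or to trial procedures. Section 5.2.1 counts events related to a mandated intervention as adverse events. Sections 5.3.1 and 5.4.2.1 use causation by a mandated intervention as the reporting criterion, but only for serious events before the first dose.

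**The concern.** A summary by relation to the procedure needs a variable that records that relation. The protocol defines none for events after dosing starts. A NO to the drug question does not supply it, because it does not say whether the cause was the puncture, the disease or something else. A later analysis plan can define tables, but it cannot create an investigator judgment that was never collected.

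The events concerned are not rare. Section 5.1.1 names procedural pain and post-lumbar puncture syndrome as the most commonly reported events in the Phase I/IIa study. Section 5.1.1.1 adds "headache, which occurred after 10% of procedures" and describes these headaches as mostly mild and transient.

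Two recording rules make the gap harder to close afterwards. Table 5 leans towards drug-related and does not prompt the investigator to consider the procedure. Section 5.3.5.1 has events during or within 24 hours after dosing entered as separate signs and symptoms, not as a diagnosis. An early post-puncture headache may therefore be coded simply as headache.

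**Working it through.** This is mainly a consistency check. There is no power or sample size figure to reproduce.

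**1. Promise against data**

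| Section | What it needs or collects |
|---|---|
| 6.7 | Relation to drug or procedure, all adverse events |
| 5.5.1 | Relation to drug or trial procedures, serious events |
| 5.3 | Causality as in Section 5.3.4 |
| 5.3.4, Table 5 | Relation to drug only, yes/no |
| 5.3.1, 5.4.2.1 | Causation by a mandated intervention, serious events before first dose only |

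The procedure relation is needed in two places, and no section defines its collection after the first dose.

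**2. How common the events are (Sections 5.1.1 and 5.1.1.1)**

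- Phase I/IIa, 34 + 12 = 46 patients: the stated 54% matches 25/46 = 54.3%, and the stated 37% matches 17/46 = 37.0%.
- Open-label extension, possible post-puncture events within 72 hours: 13/23 = 56.5% on Q4W (printed as 56%) and 12/23 = 52.2% on Q8W.
- Open-label extension, post-lumbar puncture syndrome: 4/23 = 17.4% and 3/23 = 13.0%.

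**3. Upper bound on headaches**

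Table 1 schedules 13 injections per patient, and Section 4.5.5 adds a puncture without dosing at Week 101, so 13 + 1 = 14 punctures. With 660 patients and headache after 10% of procedures:

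660 × 14 × 0.10 = 924.

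This assumes that every patient attends every puncture and that the Phase I/IIa rate carries over. Section 6.2 assumes 15% (active) and 20% (placebo) treatment discontinuation, so at that rate the real count would be lower.

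**4. What the randomised comparison still delivers**

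Injections per arm from Table 1: Q8W 2 + 11 = 13; Q16W 2 + 5 + 6 = 13; placebo 2 + 11 = 13. Procedure exposure is equal by design.

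With 220 per arm, the 95% half-width of an active-placebo difference at background rate p is 1.96 × √(2p(1 − p)/220):

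- p = 0.37: 1.96 × √(2 × 0.37 × 0.63/220) = 0.090, or 9.0 points.
- p = 0.54: 1.96 × √(2 × 0.54 × 0.46/220) = 0.093, or 9.3 points.

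The power to detect a 14-point excess (normal approximation, two-sided 5%) is about 84% for 37% against 51%, and about 86% for 54% against 68%. The arms can therefore show a moderately large drug excess over the procedural background without any attribution.

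**The case against.** The strongest reply is that the trial does not need attribution to protect its safety conclusions. Placebo patients have the same punctures and injections without the drug, under blinding, so the all-cause comparison by arm and preferred term isolates drug excess. This stands. A reader might infer from the missing item that procedural and drug harm cannot be separated at all; the documents do not support that.

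Nor is attribution the only route to procedural harm, as a reader might also infer. Section 5.1.1 itself reports such harm by term and by a 72-hour window, and the placebo arm gives a rate for procedure plus background. The 24-hour symptom rule weakens the route by term but leaves the other two.

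It is also fair that Table 5's etiologies are only examples and that Section 5.3.4 tells investigators to weigh factors unrelated to treatment. An investigator may answer NO for a puncture headache, so it is not shown that such events become drug-related in every arm. What remains is that a NO still does not record the procedure as the cause.

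Finally, the eCRF is not shown. The references to procedure relation in Sections 5.2.1, 5.5.1 and 6.7 fit a field that Section 5.3.4 simply failed to mention as well as they fit data never collected.

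**Conclusion.** The point holds as a gap between a promised summary and the data that the protocol defines for it. Section 6.7, and Section 5.5.1 for serious events, rely on a judgment about the procedure that Section 5.3.4 and Table 5 do not ask for. The loss is event-level attribution to the lumbar puncture and intrathecal injection, for the kinds of event most often reported in Phase I/IIa (54% and 37% of patients). The 924 headaches are an upper bound under full attendance and do not forecast a count; the events themselves would still be recorded.

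A reader might infer that the primary estimand is affected, since Section 6.6.1 treats separately "Treatment discontinued for study drug-related reasons (e.g., treatment-related adverse event or lack of efficacy"). The documents do not support this. Section 6.6.1 sorts stops by the reason for discontinuation, Section 4.6.1 has that reason documented on an eCRF, and no passage makes the adverse event causality answer decide the class. No primary result or between-arm safety conclusion is shown to change.

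The conclusion rests on the protocol text. If the eCRF already holds a procedure item, the defect shrinks to an omission in Section 5.3.4.

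**What to change.** - In Section 5.3.4 and on the Adverse Event eCRF, add a separate yes/no item for relation to the lumbar puncture or intrathecal procedure, answered independently of the drug question. If the field already exists, cite it in Section 5.3.4.
- In Table 5, list the study procedure among the example alternative etiologies.
- Produce the Section 6.7 summary from the two items, and let Section 5.5.1 refer to the same item.

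The cost is one extra tick-box per event for an investigator who already judges causality, and a short text change in Section 5.3.4 and Table 5.

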6.8 PHARMACOKINETIC ANALYSES

For all patients in the PK population (Section 6.1), CSF and plasma concentrations of RO7234292 will be presented descriptively, including arithmetic and geometric means, median, range, standard deviations, and coefficients of variation. Nonlinear mixed-effects modeling will be used to analyze the concentration–time data for RO7234292 in CSF and plasma following IT administration. A covariate analysis will be conducted to evaluate the effect of covariates such as body weight, age, and sex on RO7234292 exposure.

Population and individual estimates of primary PK parameters (e.g., clearance, distribution volume) and secondary PK parameters (e.g., area under the plasma

concentration–time curve, average trough plasma concentration) will be computed and used to explore exposure-response relationship on primary and key secondary endpoints, as well as safety measures. The data from this study may be pooled with data from other studies conducted with RO7234292 to support the population PK/PD modeling.

Details of this mixed-effects modeling and exploration of exposure-response analysis and results will be described and reported in a document separate from the Clinical Study Report.

6.9 IMMUNOGENICITY ANALYSES

The immunogenicity analysis population will consist of all patients with at least one ADA assessment. Patients will be grouped according to treatment received or, if no treatment is received prior to study discontinuation, according to treatment assigned.

The numbers and proportions of ADA-positive patients and ADA-negative patients at baseline (baseline prevalence) will be summarized by treatment group. For those who are ADA-positive, titers will be estimated as well as antibody subtype. In addition, the numbers and proportions of ADA-positive patients and ADA-negative patients at baseline (baseline prevalence) and after drug administration (post-baseline incidence) will be summarized for patients on active treatment only. When determining post-baseline incidence, patients are considered to be ADA positive if they are ADA negative or have missing data at baseline but develop an ADA response following study drug exposure (treatment-induced ADA response), or if they are ADA positive at baseline and the titer of one or more post-baseline samples is at least is at least 4-fold greater than the titer of the baseline sample (treatment-enhanced ADA response). Patients are considered to be ADA negative if they are ADA negative or have missing data at baseline and all post-baseline samples are negative, or if they are ADA positive at baseline but do not have any post-baseline samples with a titer that is at least 4-fold greater than the titer of the baseline sample (treatment unaffected).

The relationship between ADA status and safety, efficacy, PK, and biomarker endpoints will be analyzed and reported via descriptive statistics.

6.10 BIOMARKER ANALYSES

The biomarker endpoints are described in Section [2.5](#).

A mixed-effects model repeat measurement model will be used to model the change in each primary and secondary biomarker endpoint, adjusting for the baseline endpoint, CAG repeat length, CAP score, treatment, visit, and treatment-by-visit interaction (the final list of covariates and details of the model will be specified in the SAP).

6.11 HEALTH STATUS UTILITY ANALYSIS

The health status utility endpoints are described in Section [2.6](#).

The health status utility endpoints will be summarized using tables, listings, and graphs, as appropriate. Additional statistical modeling may be considered.

6.12 OPTIONAL INTERIM ANALYSES

The Sponsor may choose to conduct one or more interim analyses for efficacy. Below are the specifications in place to ensure the study continues to meet the highest standards of integrity when an optional interim analysis is executed.

If an interim analysis is conducted, the Sponsor will remain blinded. The interim analysis will be conducted by an iDCC and reviewed by the iDMC. Interactions between the iDMC and Sponsor will be carried out as specified in the iDMC Charter.

The decision to conduct an interim analysis, along with the rationale, specification of the endpoint (e.g., clinical and/or biomarker endpoint), number of patients, and statistical details for each analysis, will be *introduced via a future protocol amendment*, which will be submitted to relevant health authorities at least 2 months prior to the conduct of the interim analysis. The iDMC Charter will document potential recommendations the iDMC can make to the Sponsor as a result of an interim analysis, and the iDMC Charter will be made available to relevant health authorities.

If there is a potential for the study to be stopped for positive efficacy as a result of an interim analysis of efficacy data, the type I error rate will be controlled to ensure statistical validity is maintained. Additional criteria for recommending that the study be stopped for positive efficacy will be added *to a future protocol amendment*.

7. DATA COLLECTION AND MANAGEMENT

7.1 DATA QUALITY ASSURANCE

The Sponsor will be responsible for data management of this study, including quality checking of the data. Data entered manually will be collected via EDC through use of eCRFs. Sites will be responsible for data entry into the EDC system. In the event of discrepant data, the Sponsor will request data clarification from the sites, which the sites will resolve electronically in the EDC system.

The Sponsor will produce an EDC Study Specification document that describes the quality checking to be performed on the data. Central laboratory data electronic data from clinic visits (see Section [7.3](#)) and electronic data obtained from the Roche HD mobile app (see Section [7.4](#)) will be sent directly to the Sponsor, using the Sponsor's standard procedures to handle and process the electronic transfer of these data.

eCRFs and correction documentation will be maintained in the EDC system's audit trail. System backups for data stored by the Sponsor and records retention for the study data will be consistent with the Sponsor's standard procedures.

